APPENDIX E

Study ID: _____

The Gent Study – Enrollment Data Entry Form

Date: _____ Age: _____ Race/ethnicity: _____

Current Gender: Male Female Trans MTF Trans FTM NB/GQ

Sex Assigned at Birth: Male Female

Gender of Sex Partners: Male Female Trans MTF Trans FTM NB/GQ

HIV Status: Positive Negative Number of oral sex partners <2 months: ____

Date of last oral sex exposure: _____

Anatomic Sites of Gonorrhea Infection and Date and Test Type:

Pharynx: Test Date: _____ **NAAT** Yes No **Culture** Yes No

NAAT Type: _____

Rectum: Test Date: _____ **NAAT** Yes No **Culture** Yes No

NAAT Type: _____

Urethra: Test Date: _____ **NAAT** Yes No **Culture** Yes No

NAAT Type: _____

Cervix/Vagina: Test Date: _____ **NAAT** Yes No **Culture** Yes No

NAAT Type: _____

Height: _____ cm

Weight: _____ kg

Medical History:

Current Medications (and doses): _____

Date & Time of Administration of Gentamicin: _____

Date & Time of Blood Draw for Gent PK and Cr: _____

Immediate reactions (if any):

APPENDIX F

Study ID: _____

The Gent Study – TOC Visit Data Entry Form

TOC Visit Date: _____ Days since Tx: _____

Symptoms since Tx:

Y or N Headache (if yes, characterize): _____

Y or N Vision Changes (if yes, characterize): _____

Y or N Changes in Hearing (if yes, characterize): _____

Y or N Tinnitus (if yes, characterize): _____

Y or N Urinary Symptoms (if yes, characterize): _____

Y or N Nausea or Vomiting (if yes, characterize): _____

Y or N Diarrhea (if yes, characterize): _____

Y or N Constipation (if yes, characterize): _____

Y or N Rash (if yes, characterize): _____

Y or N Other (if yes, characterize): _____

Sexual Activity Since Treatment:

1) Have you been intimate with any partners since treatment? Y or N
(*Intimacy includes kissing, oral-anal sex, oral-penile sex, anal-penile sex, penile-vaginal sex*)

2) Were any of your partners since treatment the same as someone you were intimate with in the 2 months prior to your pharyngeal gonorrhea diagnosis? Y or N

If Yes to #1 above, ask the following questions:

3) How many days did you deep kiss a partner since treatment? _____

4) How many partners did you deep kiss since treatment? _____

5) How many times did you perform oral sex on a penis since treatment? _____

- 6) How many male-bodied persons did you give oral sex to since treatment? _____
- 7) How many times did you rim a partner since treatment? _____
- 8) How many partners did you rim since treatment? _____
- 9) How many times did you top (i.e. insertive anal intercourse) a partner since treatment?

- 10) How many partners did you top since treatment? _____
- 11) How many times did you bottom (i.e. have receptive anal intercourse) for a partner since treatment? _____
- 12) For how many partners did you bottom since treatment? _____
- 13) How many times did you have vaginal sex with a partner since treatment? _____
- 14) How many partners did you have vaginal sex with since treatment? _____

TOC Testing Conducted and Results:

Pharynx: NAAT Result Positive Negative

Culture Done Yes No

Culture Results Positive Negative

AST results (in mcg/mL): PCN: _____ TET: _____ CIP: _____

CFX: _____ CTX: _____ AZM: _____ GENT: _____

Rectum: NAAT Result Positive Negative

Culture Done Yes No

Culture Results Positive Negative

AST results (in mcg/mL): PCN: _____ TET: _____ CIP: _____

CFX: _____ CTX: _____ AZM: _____ GENT: _____

Urethra: NAAT Result Positive Negative

Culture Done Yes No

Culture Results Positive Negative

AST results (in mcg/mL): PCN: _____ TET: _____ CIP: _____

CFX: _____ CTX: _____ AZM: _____ GENT: _____

Cervix: NAAT Result Positive Negative

Culture Done Yes No

Culture Results Positive Negative

AST results (in mcg/mL): PCN: ____ TET: ____ CIP: ____

CFX: ____ CTX: ____ AZM: ____ GENT: ____

Repeat Treatment needed? Y or N

Date of Repeat Treatment: _____

Repeat treatment given: Ceftriaxone 250mg IM + Azithromycin 1g PO

Ceftriaxone 250mg IM + Doxycycline 100mg PO BID

Other: _____

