This study consists of two study visits. Once enrolled, subjects need to return 4-7 days (+/- 1day) for a test of cure (TOC) visit. At their enrollment visit, the subject will set up a TOC visit with either the study coordinator or study clinician, hand them an appointment reminder card (see Appendix C). Less than 24 hours prior to the appointment, the study coordinator will call the patient with an appointment reminder call. If the subject does not show up for their appointment, the study coordinator will call them that day to set up another TOC visit appointment.

Study Procedures

Screening & Enrollment

Pre-screening will occur by the PHSKC STD Clinic RN who reviews all patients charts to determine which services and provider(s) are warranted. Patients with untreated pharyngeal gonorrhea will be referred to the study coordinator for screening. Screening will occur in person by the study coordinator, study clinician or PI. We will use a standardized screening eligibility form (see Appendix D) to determine patient's eligibility. Since eligibility hinges on a diagnosis of untreated pharyngeal gonorrhea, for PHSKC STD Clinic patients, we will ask the IRB for a waiver of consent to be able to pre-screen charts to access the subject's medical record to confirm diagnosis prior to approaching the patient. All other eligibility criteria will be based on self-report. Patient will be excluded if they meet any of the following criteria:

- Age less than 16 years
- Receipt of antibiotics in ≤ 30 days
- Known allergy to any aminoglycoside
- History of renal disease (including diagnosis of solitary kidney, chronic renal insufficiency, renal cell carcinoma etc),
- Use of concurrent nephrotoxic drugs or muscle relaxants
- History of diabetes
- History of hearing loss or tinnitus
- Concurrent infection with syphilis or chlamydia
- Pregnancy and/or nursing (we will screen women not using highly active birth control, i.e. OCPs, IUD or nexplanon, who are more than 28 days from their last menstrual period)
- Unable to return for a follow-up visit 4-7 days (+/- 1 day).
- Study team's discretion

Once it has been determined that the patient is eligible for and interested in the study, the study team member will go through the informed consent with the patient in detail. After the subject has signed the informed consent, formal study procedures will begin.

1. Intake & Data Entry Form:

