Subjects will be assigned post-injection blood draw at either 30 minutes, 45 minutes or 60 minutes after the gentamicin injection in a sequential fashion, meaning that participant #1 will have a 30 minute draw, #2 a 45 minute and #3 at 60 minute. This one green top tube of blood will be tested for gentamicin concentration as part of Objective 2 and Creatinine.

5. *Counseling:*

The study clinician will counsel the subject to avoid sexual activity, and most specifically performing oral sex, deep kissing, and oral-anal sex until they return for the TOC visit.

Test of Cure Visit

Subjects will return to the PHSKC STD Clinic to meet with the study clinician 4-7 days (+/- 1 day) after their enrollment visit. The study coordinator will call the subject the day prior to the visit as a reminder. At the TOC visit:

1. *Diagnostics:*

The study clinician will obtain a pharyngeal culture for *N. gonorrhoeae* and a blood draw for a follow-up creatinine. (Specimen processing per above). If the culture is positive for *N. gonorrhoeae*, the subject will be called to return for standard of care treatment – Ceftriaxone 250mg IM plus Azithromycin 1g orally once.

2. *Behavior and Symptom screen:*

The study clinician will administer a standardized symptom screening form (see Appendix F) to assess for gentamicin side effects and tolerability. The form will also ask about sexual activity, including kissing, in the time period between treatment and TOC.

Retention Plan

The study coordinator will attempt to schedule the TOC visit at 4 days after the enrollment visit so that if the subject fails to show to that visit, there are still opportunities to reschedule the TOC visit. Additionally, although the subject will be compensated for their time in the study, they will not receive compensation until they return for the TOC visit. This is an incentive for them to keep their follow-up visit.

Data Sources and Data Management

PHSKC STD Clinic Medical Record: We will use gonorrhea test results that occurred prior to enrollment visit from the STD clinic medical record for inclusion criteria. This data will be extracted by chart review during the enrollment visit using subject name and DOB as identifiers. The information will then be entered using a subject ID in the study database. We will also use demographic and sexual behavior data from the medical record.

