Neisseria Reference Laboratory: The NRL will provide the antimicrobial susceptibility data for the *N. gonorrhoeae* isolates recovered at both enrollment and TOC visit. The culture specimens are clinical specimens and full antimicrobial susceptibility testing (AST; this includes, beta-lactamase, penicillin, tetracycline, ciprofloxacin, cefixime, ceftriaxone, azithromycin and gentamicin) is done on all isolates. However, AST is not routinely reported to the clinic. Thus, in order to obtain this data, we will submit a list of names and MRN to [name], the Director of the NRL, to pull the data for us. All personal health information (PHI) will be transferred electronically using secure file transfer technology.

Data Entry Form: The study coordinator and study clinician will record key data points on a paper data entry form which will be transcribed into electronic data entry form in RedCap. Data to be collected will come from both the STD Clinic medical record and patient interview. Data points will include: date of visit, gender identity, sex assigned at birth, age, race, height, weight, site of infections pre-enrollment and type of test used to diagnosis; time of administration of gentamicin, time of gentamicin concentration blood draw; results of treatment visit testing (culture results at each site); date of TOC visit, symptoms since treatment; sexual activity since treatment (including kissing, oral-anal, oral-penile, anal-penile, penile-vaginal etc); anatomic sites tested by culture and results; repeat treatment needed etc (see Appendices E and F)

UW Lab Medicine Research Testing Services: RTS will test our blood specimens for pre- and post- treatment Creatinine and gentamicin levels. We will give the specimens to them with study id's and dates on them, and they will provide the data via an excel file with only study ID and results.

Data Management

We will use RedCap to collect and store all study data. Data can be exported from RedCap as a Stata database, which will be used for analysis. Upon export from RedCap, we will remove identifiers except for subject ID and maintain a separate database to link subject identifiers/contact info to subject ID.

Study Confidentiality and Security

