Related: The AE is clearly related to the study procedures.

AEs are identified at the TOC visit using the symptom screen, and with Creatinine monitoring.

SAEs and specific procedure-associated AEs are reported to the Medical Monitor within 24 hours. In addition, all AEs are reported according to the University of Washington AE reporting guidelines.

MANAGEMENT OF RISKS TO SUBJECTS

Expected AEs

Expected AEs associated with gentamicin include:

- Pain at injection site
- Bruising at injection site

AE Management

- Warm compresses as needed
- Tylenol as needed

DATA ANALYSIS PLANS

The Medical Monitor will conduct interim analyses after we have primary outcome results for 10 and 25 subjects. (Enrollment will pause until analyses can be conducted). Stopping rules include the primary end point (i.e. pharyngeal cure rate), and adverse events. If after 10 and 25 subjects, the cure rate is $\leq 44\%$ (99% CI 17% – 74%; i.e. 11 persons of 25 persons with a positive culture on treatment date fail treatment), we will stop the study. We chose these numbers using the O'Brien-Fleming method of alpha spending for multiple analyses, assuming an alpha of 0.003 for the first analysis and an alpha of 0.049 for the final analysis. Using the 99% CI obtained with 11/25 treatment failures, the upper bound is less than 75%. (Our hypothesis is that gentamicin alone will be 80% effective for pharyngeal gonorrhea, with the goal to use it in combination with a second agent). Alternatively, if at interim analysis more than 20% of subjects (99% CI 20% - 46%) have a greater than 40% increase in their creatinine from baseline, we will halt the study.

Data Analysis

The proposed study aims to evaluate the efficacy of a single intramuscular (IM) dose of 360 mg of gentamicin in the treatment of pharyngeal gonorrhea. Secondary objectives include evaluating the renal safety and tolerability of 360mg of gentamicin, *documenting peak serum gentamicin levels by subject weight*, and estimating the ideal pharmacodynamic criterion using a combination of peak gentamicin concentration levels compared to MIC and treatment outcomes. *In exploratory analyses*, we will attempt to determine whether gentamicin-monotherapy induces antimicrobial resistance among treatment failures. The specific aims are:

- 1) Determine the proportion of persons whose pharyngeal gonococcal infections are cured with a single dose of 360mg gentamicin intramuscularly alone.

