APPENDIX D

Eligibility Screening Form

From Pre-screening Chart Review:

Pharyngeal Gonorrhoea Positive? Y or N

Date of Pharyngeal gonorrhoea test: _____

Chlamydial infection? Y or N (*If yes, patient not eligible*)

Syphilis infection? Y or N (*If yes, patient not eligible*)

Researcher: Is it alright with you if I ask you some questions in order to assess your eligibility for the study? Some of the questions are personal in nature.

Yes No

If the potential subject answers yes above, complete the following questions. Please check the boxes at left to indicate the question has been asked. Answer the question to the Right. Eligibility criteria are in italics following the question. You may stop the interview if, based on a single question, they do not meet eligibility criteria

Are you 16 years old or older? Yes

Do you speak and read in English? Yes

Have you taken any antibiotics (e.g. Keflex, bactrim, penicillin etc) in the past 30 days? Y or N (*If yes, they are not eligible*)

Are you allergic to any antibiotics? If so, which ones? _____ (*Allergy to gentamicin, spectinomycin, kanamycin, netilmycin, streptomycin, amikacin or tobramycin is an exclusion criteria.*)

Do you have kidney disease? Kidney diseases include renal failure (including dialysis); diagnosis of solitary kidney, renal cell carcinoma etc. (*Report of any renal disease is cause for exclusion.*)

Do you have Diabetes? Y or N (*Patients with diabetes are not eligible*).

Do you have a history of hearing loss or tinnitus? Y or N (*Patients with these symptoms are ineligible*).

What medications do you take on a regular basis? (*Potentially nephrotoxic drugs such as, Lisinopril, lithium and muscle relaxants, are cause for exclusion. If questions about certain drugs, call study PI.*)

List Here:

Are you able to return to the PHSKC STD Clinic in 4-7 days for a TOC visit? (Yes)

Study personnel:

In your estimation is the potential subject able to comply with the study procedures? Yes

Study personnel conducting screening: _____

If female-bodied patient, do urine pregnancy test. Record result here: Positive Negative

Ineligible if pregnant.

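### Antibiotics taken between gentamicin dosing and the test-of-cure culture are neither recorded nor handled in the analysis, so clearance by another drug would count as a gentamicin cure

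*Combined protocol and SAP*

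**What the plan says.** Before dosing, the plan asks about other antibiotics.

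- The exclusion criteria, in the opening summary and again under Screening & Enrollment, include "Receipt of antibiotics in ≤ 30 days".
- The eligibility form (Appendix D) asks "Have you taken any antibiotics (e.g. Keflex, bactrim, penicillin etc) in the past 30 days", and a yes makes the patient ineligible.
- The enrollment form (Appendix E) has a field for "Current Medications (and doses").

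After dosing, it does not.

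- The Behavior and Symptom screen at the Test of Cure Visit covers side effects and adds: "The form will also ask about sexual activity, including kissing, in the time period between treatment and TOC".
- The data points under Data Sources and Data Management run "date of TOC visit, symptoms since treatment; sexual activity since treatment", followed by sites, culture results and repeat treatment.
- Appendix F follows the same pattern: the block "Symptoms since Tx", 14 numbered questions on sexual activity, and test results. Its only treatment item is "Repeat Treatment needed? Y or N" with the regimen given, which concerns retreatment after the TOC result.

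Aim 1 is the proportion "cured with a single dose of 360mg gentamicin intramuscularly alone". Under Data Analysis, a negative TOC culture is a cure and a positive one is a failure. The only stated exclusion from analysis is a negative gonorrhoea test at enrollment.

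**The concern.** The outcome is a single culture taken 4 to 7 days after dosing, plus or minus 1 day, so between day 3 and day 8. An antibiotic obtained elsewhere in that interval could clear the pharynx, and the result would be credited to gentamicin. The error can only raise the cure rate.

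Data capture is also one-sided. The TOC form asks in detail about exposure after treatment, which could explain an apparent failure. It asks nothing about other antibiotics, which could produce an apparent cure. A misclassified subject would also enter the Cure column of Table 2 and the peak/MIC analysis.

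**Working it through.** **Step 1. Is the information captured anywhere else?**

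- The free-text Other line in Appendix F belongs to the symptom list and does not ask about drugs.
- The medical record is to be used for gonorrhoea tests before enrollment and for demographic and sexual-behavior data. No check of later prescriptions is planned.
- Counseling at enrollment covers sexual activity only.
- Appendices B and C were not in the text available. The appendix list gives them as the study info card and the appointment reminder card, which are unlikely to hold this item.

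**Step 2. Does the analysis deal with it?** No. The text's denominator is treated subjects who returned. The displayed formula uses subjects with a positive throat test at enrollment who received gentamicin. Neither removes or reclassifies a subject who took another antibiotic.

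**Step 3. Average size of the bias.** The plan gives no figure to reproduce. Let p be the true gentamicin cure rate and q the share who take another antibiotic that always clears the infection, with use unrelated to gentamicin outcome. Then

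observed cure = p + (1 − p)q.

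The 80% is the plan's hypothesis and 44% its stopping threshold. The values of q are assumptions.

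| True p | q = 2% | q = 5% | q = 10% |
|---|---|---|---|
| 80% | 0.80 + 0.20 × 0.02 = 80.4% | 81.0% | 82.0% |
| 44% | 0.44 + 0.56 × 0.02 = 45.1% | 46.8% | 49.6% |

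**Step 4. Weight of one subject.** One subject is 1/25 = 4 points at the 25-subject look and 1/10 = 10 points at the 10-subject look. Taking the stopping rule as its stated percentage, 11/25 = 44% stops the study and 12/25 = 48% does not, so one misclassified cure could matter at that boundary.

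**Step 5. How the handling changes the result.** Suppose 60 evaluable subjects and 48 negative cultures: 80.0% (exact 95% CI 67.7 to 89.2). Suppose k of those 48 had taken another effective antibiotic (k is assumed).

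| k | Excluded | Counted as not cured |
|---|---|---|
| 1 | 47/59 = 79.7% (67.2 to 89.0) | 47/60 = 78.3% (65.8 to 87.9) |
| 3 | 45/57 = 78.9% (66.1 to 88.6) | 45/60 = 75.0% (62.1 to 85.3) |
| 5 | 43/55 = 78.2% (65.0 to 88.2) | 43/60 = 71.7% (58.6 to 82.5) |

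**Step 6. Why one analysis is not enough.** Take p = 80% and q = 5%.

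- If use is unrelated to gentamicin outcome, exclusion recovers 80%, and counting users as not cured gives 0.80 × 0.95 = 76%, which is too low.
- If every user is someone gentamicin had failed, the unadjusted rate is 0.80 + 0.05 = 85%, exclusion gives 0.80/0.95 = 84.2%, and counting users as not cured recovers 80%.

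In both cases the two analyses span the true value.

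**The case against.** The case for leaving the plan alone is that the effect should be slight. The interval is short, and the coordinator aims for day 4. Known chlamydia and syphilis, two reasons for other antibiotics, are exclusions. Regular medications are asked about at screening and current ones recorded at enrollment, so an ongoing course should surface there. The Executive Summary says only parenteral third-generation cephalosporins have consistent efficacy against gonorrhoea, so many incidental antibiotics need not clear it. At p = 80%, the shifts of 0.4 to 2 points in Step 3 are small beside an interval of 67.7 to 89.2. All of this stands as an argument about size. It does not remove the gap, because rarity cannot be checked without asking.

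A reader might infer four stronger things that the documents do not support.

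- *That the 30-day exclusion exists because antibiotics clear or mask infection.* No reason is stated. The exclusion shows only that prior antibiotic use matters for entry.
- *That Aim 1 commits the plan to removing incidental co-medication.* The safety-monitoring section sets gentamicin alone against later use with a second agent, so the word may simply mean monotherapy as the study regimen. There is no internal contradiction.
- *That such subjects could never be found.* The identifying-data form holds clinic record numbers and contact details, and the link is kept until publication or December 31, 2021, whichever is sooner. A later chart review or call could find some. What holds is that no planned data would.
- *That a control arm would have exposed the problem.* A control arm would not show which subjects took another antibiotic. Only a question or a record check does.

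**Conclusion.** The point holds as a minor but real gap in data capture. Followed as written, the plan would count clearance by another antibiotic before TOC as gentamicin cure and would collect nothing to show it. The direction is upward. The likely size is small: 0.4 to 2 points at a true rate of 80%, for an assumed 2% to 10% of subjects taking a fully effective drug, with use unrelated to gentamicin outcome. It would be larger if subjects sought treatment because infection persisted (5 points at q = 5% in the limiting case of Step 6). The documents say nothing on frequency, so it cannot be claimed that this happens or that it would change the study's conclusion. No stated figure is contradicted.

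**What to change.** Add one line to Appendix F, and to the matching list of data points: *Any antibiotic taken since study treatment? Y/N; drug, date, reason.*

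Pre-specify two sensitivity analyses of the cure rate, each with its 95% CI:

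1. exclude subjects who took another antibiotic with activity against gonorrhoea before the TOC culture;
2. count those subjects as not cured.

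Activity can be judged from the susceptibility results already planned for enrollment isolates, preferably without knowledge of the TOC culture. If nobody reports such use, saying so settles the matter.

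The cost is one form line and two sensitivity rows. No dose, visit or clinical rule changes.

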We will evaluate subject's tolerability (Obj. 4) using a standardized symptom questionnaire conducted at the TOC visit. The symptoms questioned will include, but not be limited to, rash, tinnitus, decreased hearing, nausea, vomiting, diarrhea, headaches, and decreased appetite. There will also be a section for free response.

Figure 2: Schematic of Clinical Trial

PK: pharmacokinetics, (i.e. gentamicin peak level); Cr: creatinine, marker of kidney function

Responsibilities

Principle Investigator: [name] MPH
Department of Medicine, Division of Allergy and Infectious Diseases, University of Washington

Study Coordinator: [name]

Study Clinician: TBD

Medical Monitor: [name]
Professor of Medicine, Division of Allergy and Infectious Diseases
University of Washington
Director, UW AIDS Clinical Trials Unit
Associate Director, Center for AIDS Research
University of Washington and Fred Hutch

Study Communication: Harborview Medical Center – STD clinic
[name]
[name]
[contact]
[contact]
Email: [contact]

Study Site: Public Health – Seattle & King County
STD Clinic
[name]
[name]
[contact]

Recruitment and Retention of Subjects

Patients who screen positive for pharyngeal gonorrhea, with or without concomitant GC at other anatomic sites, and have not yet received treatment for this infection or other antibiotics in the past 30 days are eligible for this study. We will not exclude based on gender or HIV status. Recruitment will primarily occur at PHSKC STD Clinic, however, we will also encourage high-diagnosing partner clinics to refer eligible patients as well. We plan to enroll 60 persons with untreated pharyngeal gonorrhea for this study.

Recruitment at PHSKC STD Clinic:

We will employ several strategies to recruit at PHSKC STD Clinic.

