- 2) Evaluate the renal safety and tolerability of 360mg IM of gentamicin.
- 3) Document mean peak gentamicin levels following 360mg IM of gentamicin stratified by weight.
- 4) Estimate the best pharmacodynamics criterion (i.e. peak/MIC ratio) for pharyngeal gonorrhea treated with gentamicin *using individual* and mean peak gentamicin levels and NG isolate MIC.
- 5) Among treatment failures, *conduct exploratory analyses* comparing pre- and post-treatment MIC for evidence of induced resistance.

Analyses

The primary endpoint is the pharyngeal cure rate – that is, the proportion of subjects who return for TOC who clear their infections as evidenced by a negative culture 4-7 (+/-1) days after treatment. The cure rate will be calculated as the number of cured subjects divided by the total number of subjects who received treatment and returned for follow-up testing in a modified an intention to treat (mITT) analysis. We will also calculate the 95% CI for this proportion.

$$\text{Cure rate} = \frac{\text{number of subjects with negative pharyngeal culture at TOC}}{\text{number of subjects with + throat test at enrollment \& received gentamicin}}$$

Persons who test negative for NG at their enrollment visit (i.e. infection cleared between initial clinical screening test and enrollment) will be excluded from analysis. Treatment failure will be defined as a positive culture 4-7 (+/-1) days after treatment.

For our second objective, we will obtain pre- and post-treatment serum creatinine. An elevation of >40% will be considered significant. We will evaluate subject's tolerability (Obj. 2) using a standardized symptom questionnaire (see Appendix F) conducted at the TOC visit. The symptoms questioned will include, but not be limited to, rash, tinnitus, decreased hearing, nausea, vomiting, diarrhea, headaches, and decreased appetite. There will also be a section for free response.

Our third objective is to document the pharmacokinetics of 360mg of IM gentamicin by weight. We will obtain serum gentamicin levels at 30, 45 and 60minutes post dosing based on previous studies that estimated that IM gentamicin peaks between 30-60 minutes post-dose.

We will stratify the results by time post-dose, as well as by subject weight in kilograms (categorized).

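### The test-of-cure symptom form has no named item for injection-site pain, injection-site bruising or decreased appetite, so these events are likely to be under-reported relative to the symptoms it does ask about

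*Combined protocol and SAP*

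**What the plan says.** - **Expected events.** Under Management of Risks to Subjects, the list opened by "Expected AEs associated with gentamicin include" has two entries: "Pain at injection site" and "Bruising at injection site".
- **How events are found.** Collection and Reporting of SAEs and AEs states: "AEs are identified at the TOC visit using the symptom screen, and with Creatinine monitoring".
- **Which screen.** Test of Cure Visit, item 2, has the study clinician administer a standardized form to assess side effects and tolerability, and cites Appendix F. Data Analysis, Analyses, cites the same form for tolerability.
- **What it should ask.** Data Analysis, Analyses, gives a non-exhaustive list: "rash, tinnitus, decreased hearing, nausea, vomiting, diarrhea, headaches, and decreased appetite". It adds a free-response section. The Statistical Analysis Plan at the front of the protocol gives the same list and the same addition.
- **What it does ask.** Appendix F has yes/no lines for headache, vision changes, changes in hearing, tinnitus, urinary symptoms, nausea or vomiting, diarrhea, constipation and rash ("Y or N Rash (if yes, characterize"). One open Other line follows.
- **What is reported.** The front Statistical Analysis Plan will give how many subjects, and what share, report side effects. Tolerability is part of specific aim 2.

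**The concern.** A standardized questionnaire asks every subject about each symptom in the same way. Here nine lines work like that, while the two events the protocol itself expects, and one symptom the analysis text says will be asked, depend on the subject raising them in answer to an open question. The TOC window of 4-7 days, plus or minus one, means this happens 3 to 8 days after the injections.

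An event that must be volunteered tends to be recorded less often than one that is asked about. Aim 2 would then show prompted and unprompted proportions together, with the local effects of two 4 mL gluteal injections among the unprompted. A subject whose only complaint was injection-site pain, and who did not mention it, would be counted as having no side effect. With one arm, there is no control group recorded in the same way to compare against.

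**Working it through.** No figure in the plan needs reproducing. The check compares Appendix F line by line with the two lists it should serve.

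| Event | Source in the text | Named line on Appendix F? |
|---|---|---|
| Injection-site pain | Expected AEs | No |
| Injection-site bruising | Expected AEs | No |
| Rash | Analyses | Yes |
| Tinnitus | Analyses | Yes |
| Decreased hearing | Analyses | Yes (changes in hearing) |
| Nausea | Analyses | Yes (shared line) |
| Vomiting | Analyses | Yes (shared line) |
| Diarrhea | Analyses | Yes |
| Headaches | Analyses | Yes |
| Decreased appetite | Analyses | No |

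**Coverage.** Expected AEs prompted: 0 of 2. Promised symptoms prompted: 7 of 8. Those seven occupy six lines, because nausea and vomiting share one. Vision changes, urinary symptoms and constipation make up the rest: 6 + 3 = 9 named lines.

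**Other places an injection-site event could be recorded.**
1. The Other line on Appendix F, which is an open question.
2. The immediate-reactions field on Appendix E. This is free text on the enrollment form. Subjects have blood drawn 30, 45 or 60 minutes after dosing, so there is contact after the injection. The field cannot record pain that persists, or bruising that appears, after the subject has left.
3. Creatinine, the other stated means of finding AEs, cannot show any of the three events.

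**Direction.** Let p be the true proportion with an event and c the share of those events that the open fields capture. Ignoring false reports,

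reported proportion = p × c.

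This equals p only when c = 1 and is otherwise lower. The relative shortfall is 1 − c, whatever p is.

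**Size.** The documents give neither p nor c, so the size is not determined. Purely as an assumption, take p = 30%, which is 0.30 × 60 = 18 of the planned 60 subjects:

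| Assumed c | Reported proportion, 30% × c |
|---|---|
| 25% | 7.5% |
| 50% | 15% |
| 75% | 22.5% |
| 100% | 30% |

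These values apply to a single item. The share of subjects with any side effect moves less, because a subject who does not mention injection-site pain but answers yes to headache is still counted.

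**The case against.** The strongest reply is that the events can still be recorded. A clinician administers the form, the Other line puts an open question to every subject, and the text calls its symptom list non-exhaustive and provides for free response. Identifying AEs through the screen is then literally satisfied. This stands, and it rules out saying that under-counting is certain. It does not remove the likely direction of the bias, because the text offers free response in addition to the named symptoms, not in place of one of them.

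A second reply is that the omissions differ in kind. This also stands. Decreased appetite is a mismatch between the text and the form. No section promises a named injection-site question: those events appear in the risk-management section, not in the tolerability analysis. For them the point is a design recommendation, based on the protocol expecting the events and relying on this form to find them.

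Third, little depends on it. The primary endpoint is culture cure, the quantified stopping thresholds concern cure rate and creatinine, no comparison of one symptom with another is planned, and hearing, tinnitus and rash are all prompted. That limits the importance of the point, but tolerability remains a stated aim.

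A reader might also infer that injection-site reactions are the most frequent events to come. The documents call them expected but give no frequencies, so that does not follow. Nor is the shared nausea-or-vomiting line a defect: the space to characterize a yes answer lets the clinician record which occurred.

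**Conclusion.** The point holds in a limited form. Appendix F, as written, does not ask about either listed expected AE, or about one of the eight symptoms the analysis text says will be asked. The reported proportions for these three events are likely to be biased low relative to the solicited symptoms.

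This rests on one assumption beyond the documents: that open questions capture fewer events than named ones. If capture were complete, there would be no bias. The size cannot be derived from the documents, and the range under working is an illustration only.

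A reader might go further and conclude that tolerability as a whole will be under-counted, or that the side-effect results will be invalid. The documents do not support that: the open line and the enrollment-visit field may capture some or all of the events, and seven of the eight promised symptoms are asked about directly. The cure rate, its confidence interval and the creatinine stopping rule are untouched.

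**What to change.** Add three yes/no lines to Appendix F and to the matching RedCap form: injection-site pain, injection-site bruising and decreased appetite, each with the same space to characterize a yes answer. Keep the Other line. Report the three with the other solicited symptoms, and label anything recorded only under Other as unsolicited.

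Make the change before the first TOC visit, because symptoms that were not asked about cannot be recovered reliably later. If visits have already taken place, report the three items separately by form version, each with its own denominator.

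The cost is three lines on a form and three database fields, with no added visit, specimen or staff. The downside is a slightly longer interview and possibly a higher reported side-effect proportion.
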